We propose to recruit 350 patients to obtain a final sample of 300 cases with baseline and follow-up data who are randomized to one of three study groups: 1) six sessions of CBT for anxiety reduction (CBT-AR); 2) six sessions of CBT for anxiety-alcohol de-coupling (CBT-DC); or, 3) the original CBT from the parent R01 with three sessions devoted to anxiety reduction and to anxiety-alcohol de-coupling each (CBT-O). To enhance feasibility of the renewal work and ensure its continuity/interpretability with the parent R01, the population and procedures of the proposed work are matched to those used in the parent R01. In brief, alcohol dependent individuals with a co-occurring anxiety disorder will be enrolled within one week of beginning the 28-day residential alcohol use disorder (AUD) treatment program, "Lodging Plus." Patients will undergo five significant assessments: 1) Baseline Assessment (after being deemed eligible but prior to randomization); 2) Post-Treatment Assessment (immediately following the conclusion of the six-session treatment and prior to being discharged from Lodging Plus); 3) One-Month Follow-Up Assessment (30 days following completion of the study treatment); 4) Four-Month Follow-Up Assessment (120 days following completion of the study treatment); and, 5) Eight-Month Follow-Up Assessment (240 days following completion of the study treatment). Primary alcohol outcomes measures will include categorical variables (any alcohol use) and percent or count variables (e.g., days drinking, drinks per drinking occasion). We will also measure alcohol dependence and hazardous drinking statuses at follow-ups. Predictions are based on the parent R01 findings suggesting (but not demonstrating) a dose-dependent positive relationship for de-coupling therapy elements but not anxiety reduction therapy elements in terms of alcohol outcomes; i.e., CBT-DC > CBT-O > CBT-AR on alcohol outcomes. As a means of confirming that the therapeutic mechanisms targeted were responsible for the group differences obtained, process measures of the therapeutic mechanisms are included at all assessments both to verify their dose-dependent activation in groups and to track temporal patterns of change on the mechanisms relative to the outcomes over follow-ups.

Study Aims:

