6.7. Study Duration

6.7.1. Grant funding period. The grant is being funded for a period of 60 months (5 years). (See Table 2 above)

6.2.2. Projected timeline of grant-related activities. See Table 1 above for the projected timeline of all primary study phases.

6.8. Measures. All assessments (except for the qualifying assessment) are identical. However, the timeframe around which interview questions are posed refers to "since your last assessment.

6.8.1. Screen for current intoxication. If we suspect that a patient is intoxicated, blood alcohol concentration will be measured using the AlcoMate Core Breathalyzer measures BAC% between 0.00% and 0.40% in 0.01% steps. Sensor accuracy of the AlcoMate is +/- 0.005% BAC. This measure will be taken prior to any study related interactions with patients to insure they are not intoxicated at the time. If a patient's BAC is above .04% scheduled tasks for that day will be rescheduled. If the patient is driving their self, alternative arrangements will be made for their transportation home and arrangements will be made with parking services to allow their car to remain on the facilities for up to 24 hours at no cost to the patient.

6.8.2. The Structured Clinical Interview for DSM IV (SCID): The SCID (First et al., 1989) will be used to establish all relevant study diagnoses during the STUDY000005170 screening process and at follow-up appointments. Diagnostic modules include panic disorder (with or without agoraphobia) (PD), social anxiety disorder (SAD), generalized anxiety disorder (GAD), major depressive disorder (MDD), post-traumatic stress disorder (PTSD), alcohol dependence (AD) and drug *dependence* (DD). The SCID will also be slightly modified to establish a "principal" anxiety disorder (PD, SAD, or GAD) for those participants with more than one of the inclusionary anxiety disorders (Andrews et al., 2002). A qualified SCID trainer (includes the PI and Co-I, [name]) will be responsible for training the *blinded assessor* in the valid use of the SCID using standard training materials (First et al., 1989). All diagnostic decisions will be made using a clinical consensus model with the PI adjudicating any cases in which the team could not reach consensus. All interviews will be videotaped and 15% will be double-scored to index reliability (Co-I, [name] will oversee this along with therapy fidelity).

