6.15. Costs and Reimbursement of Subjects

The only costs to participants is travel to Fairview for the three follow-up assessments at 1-, 4-, and 8-month follow-ups. Participants will be reimbursed for their time for all study activities. A total of \$330 can be earned for each participant that completes each study task. (The exact payment per task is shown in Table 2 above). Payments are made within one business day of the completion of each study task via a Greenphire Clincard. Reimbursements for the follow-up visits are graduated (increased for later follow-ups) reflecting the greater value of these data to the aims of the study and our experience indicating that participants' motivation to attend follow-up assessments decreases with increasing time since the initial treatment. Note participants recruited after approval of MOD00013885 will not complete the eight-month follow-up visit and will therefore be compensated up to \$230.

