7.5. Primary Aim: To compare the CBT-DC and CBT-AR groups on alcohol outcomes

We predict that the CBT-DC group will have superior alcohol outcomes compared to the CBT-AR group. The primary intention to treat (ITT) population will include all patients randomized. The per-protocol (PP) population will include patients who completed at least four of six (66%) of the therapy sessions with CBT-O patients not missing any more than one of the three AR or DC content sessions. Hypotheses based on the vicious cycle model and parent R01 findings suggest that without alcohol-anxiety de-coupling therapy, drinking relapse is more likely to occur and more severe when it does occur. Therefore, we consider as primary outcomes both categorical relapse status (yes vs. no) and continuously measurement of relapse severity (percent/number days drinking and drinks per drinking day). Secondary alcohol outcomes tested include categorical status on: a) alcohol dependence (yes vs. no) and hazardous drinking (yes vs. no). Follow-up assessments occur 1-, 4- and 8-months following the conclusion of the study therapy and are keyed to the time since the last assessment. To align study findings with the parent R01, the primary assessment point will be the 4-month FU. However, hypotheses will also be tested across all time points to establish temporal patterns of group effects. We test the hypotheses using mixed effects models if data residuals are

normally distributed and generalized estimating equations (GEE) if the data are non-normally distributed (Gueorguieva, & Krystal, 2004; Liang & Zeger, 1986). Both are flexible regression methods for incomplete repeated measures data and allow continuous and categorical covariates, fixed and time-dependent covariates, and a specification of unstructured as well as structured covariance matrix. Categorical outcomes will be evaluated using chi-square tests of proportions and logistic regression, with statistical significance criterion also set at $p < 0.05$. Zero-inflated negative binomial analyses will be used to contrast the study groups on count variables if warranted by a high percentage of zero alcohol use days over the follow-up (e.g., Agresti, 2002).

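### The across-time reading of yes/no drinking outcomes confounds time with look-back windows of about 30, 90 and 120 days, and the 8-month point rests on earlier recruits only

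*Combined protocol and SAP*

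**What the plan says.** Section 7.5 names yes/no relapse as a primary outcome alongside drinking days and drinks per drinking day. Dependence and hazardous drinking, both yes/no, are secondary. The 4-month visit is primary, and the section continues: "However, hypotheses will also be tested across all time points to establish temporal patterns of group effects".

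The look-back rule is in the same section: "Follow-up assessments occur 1-, 4- and 8-months following the conclusion of the study therapy and are keyed to the time since the last assessment". Section 6.8 (Measures) agrees: "the timeframe around which interview questions are posed refers to" the period since the last assessment. The Design Overview dates the visits: "One-Month Follow-Up Assessment (30 days following completion of the study treatment"), "Four-Month Follow-Up Assessment (120 days following completion of the study treatment") and "Eight-Month Follow-Up Assessment (240 days following completion of the study treatment").

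Section 6.8.3 takes every alcohol outcome except SCID dependence from the Timeline Follow-Back (TLFB), a day-by-day calendar. It expresses drinking days as a percentage or as a number per month.

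Sections 5.1 and 6.15 drop the last visit for later recruits: "participants recruited after approval of MOD00013885 will not complete the eight-month follow-up visit". Section 7 sets no common window for yes/no outcomes and does not mention this change.

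**The concern.** The chance of at least one drinking day, or at least one hazardous day or week, rises with the number of days looked back on. Each visit has its own window length, so a time term in a GEE or mixed model cannot separate time from window. A group effect that never changes can then differ between visits, and the reader cannot tell a real change from a product of the scoring rule. At stake is the temporal pattern that section 7.5 sets out to establish for a primary outcome.

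The 8-month visit adds a second problem of comparability. Its participants are a subset, fixed by recruitment date, of those seen at 1 and 4 months.

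**Working it through.** **Inputs.** Visit days 30, 120 and 240 after therapy (Design Overview). Relapse 53% (CBT-AR), 21% (CBT-DC) and 41% (CBT-O) at four months (sections 7.5 and 7.6). Two-sided alpha 0.05. About 300 cases with 4-month data, so 100 per arm (section 6.1).

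**The plan's own figure.** The documents give no figure for the across-time analysis, so I checked the relapse rates against the sample size. For 53% vs 21% at 80% power, the two-proportion formula gives 35 per group, or 41 with continuity correction; the plan states 41. The odds ratio is (0.53/0.47)/(0.21/0.79) = 4.24; the plan states 4.2. For 41% vs 21% I get 93 with correction; the plan states 94. The inputs are read correctly.

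**Windows.** 30 − 0 = 30 days, 120 − 30 = 90 days, 240 − 120 = 120 days. The protocol days in Table 2 (8, 40, 130, 250) give 32, 90 and 120.

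**Constant effect, no heterogeneity.** The daily rate is h = −ln(1 − p)/c, where c is the number of days to which the relapse rate p applies. The risk in a window of w days is 1 − exp(−h·w). For c = 120, h is 0.00629 (AR) and 0.00196 (DC), a rate ratio of 0.31 at every visit. The plan says four months, but the 4-month visit looks back only 90 days, so both calibrations are shown.

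| Calibration | Window (days) | AR | DC | Risk difference (points) | Risk ratio | Odds ratio |
|---|---|---|---|---|---|---|
| 120 days | 30 | 17.2% | 5.7% | 11.5 | 3.01 | 3.42 |
| | 90 | 43.2% | 16.2% | 27.0 | 2.67 | 3.94 |
| | 120 | 53.0% | 21.0% | 32.0 | 2.52 | 4.24 |
| 90 days | 30 | 22.3% | 7.6% | 14.7 | 2.94 | 3.50 |
| | 90 | 53.0% | 21.0% | 32.0 | 2.52 | 4.24 |
| | 120 | 63.5% | 27.0% | 36.5 | 2.35 | 4.70 |

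**Between-patient heterogeneity.** The documents give none, so I assumed gamma-distributed rates with variance θ. The window risk is 1 − (1 + θ·m·w)^(−1/θ), with m set so that the risks are 53% and 21% at 120 days.

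| θ (assumed) | Odds ratio at 30/90/120 days | Risk difference (points) |
|---|---|---|
| 0.5 | 3.82 / 4.10 / 4.24 | 13.5 / 28.2 / 32.0 |
| 1 | 4.24 / 4.24 / 4.24 | 15.8 / 29.2 / 32.0 |
| 2 | 5.12 / 4.44 / 4.24 | 20.3 / 30.6 / 32.0 |
| 4 | 6.46 / 4.61 / 4.24 | 27.8 / 32.0 / 32.0 |

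**Chi-square power at each visit.** CBT-O vs CBT-DC, 41% vs 21% over 90 days, 100 per arm at every visit (generous at 8 months), constant effect:

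| θ | 30 days | 90 days | 120 days |
|---|---|---|---|
| 0 | 47% | 87% | 93% |
| 1 | 60% | 87% | 90% |
| 2 | 72% | 87% | 88% |
| 4 | 86% | 87% | 85% |

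**8-month numbers.** The documents do not say how many were recruited after MOD00013885. If 20 to 100 of 350 were (assumed), (350 − number) × (300/350)/3 leaves about 94 to 71 per arm.

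**The case against.** The strongest reply is that logistic regression works on the odds-ratio scale, where the distortion is small against sampling error. Take the 90-day calibration without heterogeneity, 100 per arm and independent windows. The log odds ratio differs between 1 and 8 months by ln(4.70/3.50) = 0.295, with a standard error of about 0.54. An arm-by-time test would reject about 8% of the time against a nominal 5%. That stands: a formal interaction test would seldom report a false trend for the Primary Aim contrast. It does not settle the matter, because section 7.5 also plans chi-square tests of proportions, and a pattern of non-significant at 1 month and significant at 4 can arise with no change in effect.

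Four stronger readings are tempting, and the documents do not support them:

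- **That a constant effect will always look as if it grows.** The risk ratio falls in every scenario above, and the odds ratio can go either way.
- **That all primary outcomes are affected.** Percent days, days per month and drinks per drinking day do not accumulate with window length.
- **That dropping the 8-month visit manufactures a late effect.** It follows recruitment date, not arm, and section 7.3 randomises in permuted blocks. The repeated-measures methods named in section 7.5 also accept incomplete data. What is missing is a statement of how the earlier and later recruits will be compared.
- **That the 4-month primary comparison is biased.** Both arms share one window at each visit.

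**Conclusion.** The point holds for any use and hazardous drinking when visits are compared with each other. Under a constant effect the risk difference, and the chance of a significant chi-square test, typically rise from 1 to 4 months. For 53% vs 21% without heterogeneity the risk difference goes from 11.5 to 27.0 points, or from 14.7 to 32.0 under the 90-day calibration. The rise weakens as heterogeneity grows; at the highest assumed value the chi-square pattern disappears and the odds ratio suggests a fading effect instead. Direction therefore depends on the scale and on an unknown quantity, so the planned temporal pattern cannot be interpreted as written.

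The sizes rest on constant rates within each arm, the plan's relapse assumptions and the heterogeneity values I assumed. The unequal windows themselves follow directly from the documents. SCID dependence shares the look-back rule, but these calculations do not model a diagnosis. The 8-month cohort is a separate matter of population and precision. None of this touches the primary 4-month test; it is a cheap improvement worth making before analysis.

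**What to change.** For the across-time analysis only:

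1. Score any use and hazardous drinking from the daily TLFB in equal windows, for example consecutive 30-day periods, and test arm by period. A discrete-time hazard of first drink is an alternative for any use. In the no-heterogeneity example calibrated to 120 days, every 30-day period then shows 17.2% vs 5.7%, a difference of 11.5 points and an odds ratio of 3.42, so a constant effect looks constant.
2. Compare 4 with 8 months only in participants scheduled for both visits, or add a before/after-MOD00013885 term to the repeated-measures model. Report how many participants fall on each side.
3. Report SCID dependence by visit, without reading a trend across windows of unequal length.

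The 4-month primary analysis stays as it is. The cost is a few sentences in section 7.5 and reprogramming of data already collected. The drawback is fewer events per window: in the same example with 100 per arm, power within a single 30-day window is about 72%, against 99% for the 90-day window. The evidence should therefore come from the model across periods, not from separate tests in each.

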6.8.3. The Time Line Follow-Back (TLFB). The TLFB interview (Sobell & Sobell, 1995) will be used to identify daily drinking patterns of patients in the four months before treatment and in the intervals between study assessments. The TLFB has been shown to have adequate psychometric *qualities* in both clinical and non-clinical populations (Sobell & Sobell, 1995). Using a calendar, the respondent provides retrospective estimates of daily drinking over a specified amount of time. All primary and

secondary alcohol outcomes, with the exception of alcohol dependence from the SCID, will be derived from the TLFB assessment including: 1) any use vs. abstinence; 2) *percent or number (depending on the distribution) days drinking per month*; 3) *number of drinks per drinking day; and, 4) NIAAA-defined “hazardous drinking” (for men: > 4 drinks in a day or 14 drinks in a week; for women: > 3 drinks in a day or 7 drinks in a week) status.*

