7.2. Data quality/integrity

All data will be inspected for missing and outlier values and response set patterns. Distributions will be graphically represented and inspected visually and quantitatively for departures from normality and other irregularities. All data will be characterized in terms of means, standard deviations, histograms, and response ranges for continuous variables and frequencies and counts for categorical variables. A random sample of 5% of cases will have all hard copy data compared to entered data for accuracy, including all measures scored by computer algorithms. The need for data re-entry or recoding, data transformations and non-linear or non-parametric analyses will be based on these results.

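### The model for the primary drinking-severity outcomes is picked from the observed data, and no deciding test is named if the zero-inflated model is used

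*Combined protocol and SAP*

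**What the plan says.** Section 7.5 treats relapse (yes or no) as primary and, next to it, "continuously measurement of relapse severity (percent/number days drinking and drinks per drinking day"). On timing, "the primary assessment point will be the 4-month FU".

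The model for the severity outcomes then depends on what the data look like:

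- "We test the hypotheses using mixed effects models if data residuals are" normal;
- "generalized estimating equations (GEE) if the data are non-normally distributed";
- "Zero-inflated negative binomial analyses will be used to contrast the study groups on count variables if warranted", the trigger being a large share of zero-use days.

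Two other places widen the choice. Section 6.8.3 defines the drinking-days outcome as "percent or number (depending on the distribution) days drinking per month". Section 7.2, after describing the inspection of distributions, adds: "The need for data re-entry or recoding, data transformations and non-linear or non-parametric analyses will be based on these results".

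None of these sections gives a normality criterion, a threshold for the share of zeros, a GEE family or link, an order of precedence between GEE and ZINB, or the ZINB coefficient that decides the outcome. Table 1 lists data cleaning, then breaking the blind, then analysis. It does not place the choice of model in that sequence.

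**The concern.** A ZINB model yields two treatment effects: one on the odds of being a structural zero, one on the mean count among the rest. A mean-based model yields one effect, which combines the two. These are different questions, and the plan does not say which one a severity success must answer.

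The hypothesis in section 7.5 is that without de-coupling therapy relapse is both more frequent and, once it happens, worse. Either ZINB coefficient could therefore be offered as confirmation. The zero part also asks nearly the same question as the relapse outcome, which is already primary, so a severity success could be the relapse result counted a second time.

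At stake are the error rate of a primary outcome and whether its result can be read without knowing which branch was taken.

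**Working it through.** **Inputs from the plan.** Four-month relapse of 53% (CBT-AR) and 21% (CBT-DC), section 7.5; 41% (CBT-O), section 7.6; 100 analysed per group, section 7.8; two-sided 0.05.

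**Inputs assumed, because the plan gives none.** Drinking days over 120 days, zero-inflated negative binomial; mean 30 days among drinkers unless stated; dispersion 0.5 or 1.0; one time point; no dropout.

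**Step 1. Reproduce the plan's figure.** The standard two-proportion formula is n = [1.96√(2p̄q̄) + 0.842√(p₁q₁ + p₂q₂)]² / (p₁ − p₂)². With 0.53 and 0.21 (p̄ = 0.37):

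- n = (1.96 × 0.683 + 0.842 × 0.644)² / 0.32² = 34.5, so 35 per group;
- with continuity correction, 41, as stated.

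This figure concerns relapse only. Section 7 states no power for the severity models.

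**Step 2. Share of zeros.** 1 − 0.53 = 47% and 1 − 0.21 = 79%, on average 63%. A count with that many zeros will not leave normal residuals. The first switch is uninformative and the third is foreseeable.

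**Step 3. What each test measures at 53% versus 21% with equal severity.** Overall means are 0.53 × 30 = 15.9 and 0.21 × 30 = 6.3 days, a ratio of 0.40. Among drinkers the ratio is 30/30 = 1. The mean-based test has a real effect to find; the count part has none.

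**Step 4. Type I error.** For two independent tests, 1 − 0.95² = 9.75%. Simulation with 47% drinking in both arms, 2,000 trials each (Monte Carlo standard error near 5% is √(0.05 × 0.95/2000) = 0.5 points):

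| Declared positive if significant | dispersion 0.5 | dispersion 1.0 |
|---|---|---|
| Linear mean difference | 5.4% | 4.8% |
| Mean ratio, log link, robust variance | 5.5% | 5.2% |
| ZINB joint test, 2 df | 4.9% | 3.8% |
| Either ZINB part | 10.0% | 8.8% |
| Any of linear, mean ratio, either ZINB part | 12.0% | 10.9% |

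**Step 5. Rejection rates when treatment works** (dispersion 1.0, 2,000 trials each):

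| Drinking; mean days among drinkers | Linear | Mean ratio | Zero part | Count part | Joint 2 df | Relapse chi-square |
|---|---|---|---|---|---|---|
| 53% v 21%; 30 v 30 | 88.0% | 86.4% | 99.8% | 4.8% | 99.2% | 99.8% |
| 53% v 41%; 30 v 30 | 19.7% | 19.9% | 40.0% | 3.7% | 30.6% | 40.9% |
| 53% v 41%; 30 v 20 | 70.2% | 72.5% | 38.6% | 41.9% | 58.2% | 43.8% |
| 47% v 47%; 30 v 18 | 45.9% | 49.9% | 4.9% | 61.7% | 51.9% | 5.8% |

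The mean ratio and the count part reach opposite decisions in 85%, 20%, 35% and 25% of trials, row by row. The linear and mean-ratio tests disagree in only 0.3% to 4.2% of trials over all scenarios, null included. A separate run of 500 trials per scenario agreed: either ZINB part 8% to 10% under the null; at 53% versus 21%, zero part 99.8%, mean ratio 85%, count part 4%.

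**Step 6. Drinks per drinking day.** At the plan's rates, about 0.53 × 100 = 53 and 0.21 × 100 = 21 patients per arm would have a value. Section 7.5 does not say how the abstainers enter.

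**The case against.** Five counter-arguments deserve an answer.

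1. **The normality switch does little harm.** This stands. A mixed model and a GEE would nearly always give the same decision here. The fork that matters is a mean-based model versus ZINB, and then which ZINB part is read.
2. **The extra error is that of co-primary outcomes, not of ZINB.** Largely true. In a check of 1,000 trials per scenario with mean 15 days among drinkers, the zero part agreed with the relapse chi-square in 99% of trials. Under the null, either ZINB part was significant in 10.3% and 11.5% (dispersion 1.0 and 0.5), against 10.6% and 11.7% for relapse chi-square or count part. That is itself a reason not to count the zero part as a severity result.
3. **A count part significant in 4% to 5% of trials is not a failure.** Correct. With severity unchanged among drinkers, that is its proper error rate. The figure shows that the branches ask different questions, not that one is defective.
4. **Choosing by distribution is not choosing by p value.** Also correct. In the same check, a rule fixed on pooled data (count part if zeros exceed 50%, otherwise mean ratio) had null error of 4.9% and 7.4%. Nearly all of the second figure was the count test's own small-sample error (7.2%). But the plan states no such rule, and does not say that the choice precedes unblinding.
5. **The analysis tolerates incomplete data.** A reader might infer that GEE, which without weighting needs stricter missing-data assumptions than a likelihood mixed model, would bias the primary result. The documents do not support making that central. A simulation gave about 3% bias in the rate ratio with repeated measures, and about 10% with 4-month data only. Both assumed that 1-month drinkers are lost at 40% versus 15% by arm, a pattern the plan does not suggest; section 6.1 assumes 15% attrition overall.

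**Conclusion.** The point holds in a limited form. The severity model is chosen from the observed data, and no deciding test is named if ZINB is used. The plan's own relapse rates made that branch foreseeable, so the choice could have been fixed in advance.

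Reading either ZINB coefficient at 0.05 roughly doubles the type I error, to about 8% to 10%; a single named test stays near 5%. The conclusion can depend on the branch, most sharply when treatment changes relapse but not severity among drinkers.

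Two stronger readings are not supported. One is that the result must turn on the branch: linear and GEE analyses seldom disagree. The other is that the true error rate is 10% to 12%: that is an upper bound assuming free choice among all branches, which the documents do not say will happen.

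The sizes rest on assumed severity, dispersion, a single time point and no dropout. The missing rule does not rest on any of these. This should be corrected in the SAP; it does not undermine the design.

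**What to change.** Delete the residual-normality switch. Before unblinding, name one scale, one model and one test for each severity outcome at 4 months.

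- **Drinking days.** Fix the scale as number of days. Either use a single negative binomial (log-link) mean ratio with robust standard errors on all randomised patients, zeros included, or use a two-part model judged by one named test: the joint 2-df test, or the count part alone, since relapse is tested separately. Adjust for baseline drinking and the trait-anxiety stratification factor. Report the remaining components as descriptive.
- **Drinks per drinking day.** Do not apply the all-randomised negative binomial; abstainers have no value, and coding them zero would mix relapse with intensity. Either analyse it among those who drank, labelled as a descriptive, non-randomised comparison, or replace it with total drinks including zeros.
- **Missing data.** Use 1-month drinking in multiple imputation or weighting as a sensitivity analysis.

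The cost is SAP wording; both adjustment variables are already collected. The downside is some loss of efficiency if the model not chosen would have fitted better.
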